#### **9.6.5            Physical Measurements**

Not applicable.

#### 9.6.6        **Electrocardiogram**

All on-study ECG data including PR, QRS, QT, RR, QTcB, and QTcF interval will be summarized **for AML parts only. Mean  $\pm$  SE by visit graph may be plotted for QTcF and QTcB.**

Summaries over time and/or changes from baseline over time will be provided for all ECG parameters.

Subjects will be categorized into the following groups per their maximum change from baseline in QTcF. Unscheduled assessments will be included in the determination of the maximum change.

- $\leq$ 30 msec
- >30 – 60 msec
- >60 msec

The number and percentage of subjects in each group will be summarized.

Subjects will also be categorized into the following groups per their maximum post baseline QTcF. Unscheduled assessments will be included in the determination of the maximum post baseline value.

- $\leq$ 450 msec
- >450 – 480 msec
- >480 – 500 msec
- >500 msec

The number of subjects in each group will be summarized for each dosing group.

In addition, the relationship between PK concentration of AMG 176 and change from baseline in QTcF may be explored graphically **and performed by clinical pharmacology modeling and simulation (CPMS) team.**

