9.4.2.3.8 Exposure to Concomitant Medication

The number and proportion of subjects receiving concomitant medications of interest from study day 1 through safety follow-up will be summarized by preferred term as coded by the World Health Organization Drug (WHODRUG) dictionary. In addition, the number and proportion of subjects receiving anti-cancer therapies during long-term follow-up will be summarized.

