## 9.6 Safety Analyses

### 9.6.1 Analyses of Primary Safety Endpoint(s)

All the safety analysis will be performed based on full analysis set unless otherwise specified.

Table 4. Safety Endpoint Summary Table

Endpoint	Statistical Analysis Methods
Incidence of Dose-Limiting Toxicities (DLTs), treatment-related and treatment-emergent adverse events, and clinically significant changes in vital signs, electrocardiograms (ECGs), and clinical laboratory tests	

Treatment-emergent, treatment-related adverse events, vital signs, electrocardiograms, clinical laboratory tests will be performed based on full analysis set.

Incidence of dose-limiting toxicities will be based on DLT evaluable analysis set.

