**Summary statistics of troponin over time by dose level will be provided based on data availability.**

#### **9.6.4            Vital Signs**

Vital signs (systolic / diastolic blood pressure, heart rate) over time and change from baseline will be summarized. The analyses of vital signs will include summary statistics over time **for AML parts only.**

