#### **9.6.10       Exposure to Concomitant Medication**

The number and proportion of subjects receiving concomitant medications **of interest from study day 1 through safety follow-up** will be summarized by preferred term as coded by the World Health Organization Drug (WHODRUG) dictionary. **In addition, the number and proportion of subjects receiving anti-cancer therapies during long-term follow-up will be summarized. These analyses will be provided for AML parts only.**

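### SAP 9.6.6 limits the ECG summaries to the AML parts, so the ECG and QTcF tables would probably omit 360 and 480 mg/m², the myeloma-only doses with troponin elevations

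*SAP*

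**What the plan says.** **ECG.** SAP 9.6.6 begins: "All on-study ECG data including PR, QRS, QT, RR, QTcB, and QTcF interval will be summarized", followed directly by "for AML parts only". The rest of the section covers summaries of ECG parameters over time, categories of maximum QTcF change, categories of maximum post-baseline QTcF, and an optional concentration-QTcF exploration. None of it repeats or lifts the limit. The second category table reads "The number of subjects in each group will be summarized for each dosing group".

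**Vital signs.** SAP 9.6.4 has two sentences that do not agree. The first says blood pressure and heart rate "over time and change from baseline will be summarized", with no limit. The second says "The analyses of vital signs will include summary statistics over time" and adds the AML-only words.

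**General rules.** SAP 9.6.1 states: "All the safety analysis will be performed based on full analysis set unless otherwise specified". Table 4 in that section bases ECGs and vital signs on the Full Analysis Set, which includes every treated MM subject. SAP 9.1 calls for safety summaries by dose level within each indication.

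**Protocol.** Sections 9.4.2.3.4 (vital signs) and 9.4.2.3.5 (ECG) have no indication limit. SAP 2.1 and protocol Section 3 include clinically significant ECG and vital-sign changes in the primary safety endpoint for Parts 1a and 1b.

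**Declared changes.** SAP Section 10 says that the study ended early and that only selected analyses will be done. It then lists six that will not be: PFS/EFS, time to response, BAX and caspase 3, events of interest, antibodies, and prior anti-cancer therapy. ECG is not on the list.

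**The concern.** Increased troponin is one of the two identified risks in protocol 2.3.2, and protocol 2.3.2.2 names ECGs alongside cardiac enzymes as the monitoring for it. The synopsis reports troponin elevations at 360 and 480 mg/m² in MM. SAP 9.6.3 plans troponin summaries by dose level with no AML limit, subject to data availability. An AML-only ECG section would therefore put troponin at the two highest doses in the report without the matching ECG and QTcF tables.

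The category tables matter because they do not depend on an investigator's judgement. A QTcF rise of more than 60 msec, or a value above 500 msec, is counted whether or not anyone called it clinically significant. Without the tables, a QTcF increase that no one judged clinically significant at 360 or 480 mg/m² would not appear in any descriptive ECG output.

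The wording also leaves a practical problem. One programmer could follow Table 4 and include the MM subjects, and another could follow the first sentence of 9.6.6 and leave them out.

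**Working it through.** **1. Planned dose levels (protocol Table 4-1 and Sections 4.1.1 and 4.3), in mg/m².**

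| Part | Indication | Levels |
|---|---|---|
| 1a | MM | 30, 40, 50, 60, 120, 180, 240, 360, 480 |
| 1b | MM | 180, 240, 360, 480 |
| 3a | AML | 60, 120, 180 |
| 3b | AML | 120, 180, 240 |
| 3c | AML | 120 |
| 3d | AML | 60 |
| 4 | AML | 60, 120, 180, 240 |
| 5A | AML | 120, 240 |
| 5B | AML | 240 |

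The highest AML level is 240. The MM levels with no AML counterpart are 30, 40, 50, 360 and 480. Those above 240 are 360 and 480, so an AML-only table loses two of two.

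**2. Subjects.** The plan's total reproduces: 36 + 12 + 17 + 11 + 4 + 11 + 60 + 68 = 219. The MM subjects number 36 + 12 = 48, and 48/219 = 21.9% of planned enrolment. This share covers MM subjects at every dose, against a planned total for a study that stopped early. It does not measure the group at 360 and 480. For that group the documents give only one count: protocol 4.1.1 reports a troponin DLT in 2 of 8 subjects at 360 mg/m², without saying whether the 8 are all treated or only DLT-evaluable. No number is given for 480.

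**3. Scope of the limit in 9.6.6.** Two readings are possible.
- *The opening sentence governs.* It covers all on-study ECG data and names QTcF, and the later sentences read as detail of how those data are shown. The tables then stop at 240 mg/m².
- *Each sentence stands alone.* The later sentences have no limit, one table is by dosing group, and Table 4 points to the Full Analysis Set. The QTcF categories then include 360 and 480 mg/m².

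The first is the more natural reading of the paragraph, but the SAP does not state it.

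**4. What stays visible for MM on the first reading.**
- Clinically significant ECG findings are adverse events (protocol 11.4), tabulated by dose level without an AML limit (SAP 9.6.2).
- Clinically significant cardiac dysfunction and ECG changes are DLT criteria for all subjects (protocol Table 6-1).
- Troponin over time and the laboratory shift tables (SAP 9.6.3) have no AML limit.
- The optional concentration-QTcF exploration is not expressly limited.

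What drops out is the interval summaries over time and the two QTcF category tables.

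**5. Data available.** Protocol Tables 1-2 and 1-3 schedule 12-lead ECGs in Parts 1a and 1b, and Table 1-9 has them in triplicate through cycle 4. SAP Section 5 derives QTcF from the reported QT and RR, so nothing new has to be collected.

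**The case against.** The strongest reply is that this is an open scoping choice. The study was terminated early, a synopsis report is planned, MM development is paused, and doses above 240 mg/m² are no longer pursued. Section 10 warns that only selected analyses will be done, and 9.6.1 allows exceptions. The ECG mitigation in protocol 2.3.2.2 is clinical monitoring, with a site physician reviewing every tracing, and not a descriptive table. The signal at the high doses was troponin, which will still be summarised.

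Much of this stands. The restriction is written in plain view, and early termination is a fair reason for fewer tables. But the general notice in Section 10 does not say which analyses were cut beyond its six items. The exception clause in 9.6.1 permits a limit without settling how far this one reaches, and the conflict with Table 4 and SAP 9.1 remains.

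A reader might infer three stronger things that the documents do not support:
- *That a primary endpoint component is lost for MM.* It is not, because clinically significant changes are still reported as adverse events or DLTs.
- *That vital signs are restricted in the same way.* The first sentence of 9.6.4 is unrestricted, so MM vital-sign summaries are not clearly dropped.
- *That the QTcF categories certainly exclude MM.* Those sentences carry no limit, so exclusion is likely but not established.

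**Conclusion.** The point holds for the ECG section and should be fixed. On its natural reading, SAP 9.6.6 removes descriptive ECG and QTcF-category results at both dose levels above 240 mg/m², the levels with the reported troponin elevations, although ECG changes are part of the primary safety endpoint in the parts concerned. The effect is confined to descriptive output, and the number of subjects affected at 360 and 480 mg/m² cannot be derived from the documents.

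The conclusion rests on two assumptions: that the opening sentence governs the section, and that no AML subject was dosed above 240 mg/m². On the second, protocol 2.3.2.2 and 4.3.1.2.3.2 describe MM and AML experience together at the higher doses, but no AML part lists such a dose. If the first assumption fails, the problem reduces to unclear wording, and the same edit cures it. SAP 9.6.4 is an inconsistency to tidy, and the gaps in Section 10 are a documentation matter.

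**What to change.** 1. In SAP 9.6.6, delete "for AML parts only" so that the ECG summaries cover Parts 1a and 1b by dose level. At minimum, the two QTcF category tables should do so.
2. In SAP 9.6.4, delete the same words, so that its two sentences agree.
3. As housekeeping, list in Section 10 any restriction that is kept, and say whether it reaches the QTcF categories. This includes SAP 9.6.10, which ends "These analyses will be provided for AML parts only", whereas protocol 9.4.2.3.8, which plans that "the number and proportion of subjects receiving anti-cancer therapies during long-term follow-up will be summarized", has no such limit. Also list the vital-sign shift tables, which protocol 9.4.2.3.4 plans and the SAP does not; removing the AML words does not restore them.

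The cost is a SAP edit and a few extra tables from ECG and vital-sign data already collected. No protocol amendment is needed.

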#### 9.6.7        **Antibody Formation**

The incidence and percentage of subjects who develop anti-AMG 176 antibodies at any time will be tabulated.

#### 9.6.8        **Exposure to Investigational Product**

Descriptive statistics will be produced to describe the exposure to AMG 176. Number of cycles initiated, number of doses, duration of treatment, cumulative dose, average dose

delivered per day, average dose delivered per treated week, **dose intensity and relative dose intensity** will be summarized. Summaries of the number and percentage of subjects with dose modifications and reason for modification will be provided.

A listing of the unique manufacturing lot numbers and a listing of the subjects administered each manufacturing lot number will be provided.

#### **9.6.9        Exposure to Non-investigational Product(s)**

Descriptive statistics will be produced to describe the exposure to azacitidine, itraconazole. **Number of cycles initiated, number of doses, cumulative dose, average dose delivered per day, average dose delivered per treated week, dose intensity and relative dose intensity** will be summarized.

#### **9.6.10       Exposure to Concomitant Medication**

The number and proportion of subjects receiving concomitant medications **of interest from study day 1 through safety follow-up** will be summarized by preferred term as coded by the World Health Organization Drug (WHODRUG) dictionary. **In addition, the number and proportion of subjects receiving anti-cancer therapies during long-term follow-up will be summarized. These analyses will be provided for AML parts only.**

### **9.7        Other Analyses**

#### **9.7.1       Pharmacokinetic Analyses**

The analysis of pharmacokinetic endpoints will include data from all subjects who have received at least 1 dose of the investigational product and have at least 1 pharmacokinetic sample collected.

The PK parameters for AMG 176 including, but not limited to  $C_{max}$ , minimum observed concentration ( $C_{min}$ ), AUC, CL, and, if feasible,  $t_{1/2}$  will be estimated using standard non-compartmental PK methods and summarized by dose groups using means, standard deviations, medians, minimums, and maximums for intensive and peak/trough determinations. AMG 176 concentrations at each time point along with PK parameter values may be reviewed for each subject. Individual AMG 176 concentration/time profiles will be plotted by dose groups. Summary statistics will be computed for each sampling time and parameter as appropriate. For subjects in Part 3d (DDI assessment with itraconazole), AMG 176 PK parameters ( $C_{max}$ , AUC) will be compared from day 1 (with itraconazole) to day 15 (without itraconazole) to evaluate the effect of itraconazole on the PK of AMG 176, **if feasible**. Additional analyses to explore relationship between

exposure and safety and exposure and efficacy may also be performed. Pharmacokinetic parameters such as  $C_{max}$ , AUC, and  $t_{1/2}$ , if feasible, will be estimated and summarized for azacitidine.

**9.7.2 Analyses of Pharmacokinetic or Pharmacokinetic/Pharmacodynamic Endpoints**

Not applicable.

**9.7.3 Analyses of Clinical Outcome Assessments**

Not applicable.

**9.7.4 Analyses of Health Economic Endpoints**

Not applicable.

**9.7.5 Analyses of Biomarker Endpoints**

Not applicable.

**10. Changes From Protocol-specified Analyses**

The study was terminated early. Synopsis CSR will be provided, and thus selected planned analyses will be performed. The following analyses will not be performed.

1. PFS (MM), EFS (AML)
2. TTR
3. BAX and caspase 3
4. Events of interest summaries
5. Antibody formation
6. Prior anti cancer therapies

**12. Prioritization of Analyses**

There is no prioritization of analyses.

**13. Data Not Covered by This Plan**

The analyses of PK (including the DDI assessment for Part 3d) and exploratory endpoints are not covered by this plan.

## 14. Appendices

### Appendix A. Handling of Dates, Incomplete Dates and Missing Dates

#### Imputation Rules for Partial or Missing Dates for Adverse Events and Concomitant Medications

The reference date for the following rules is the date of first dose of study drug.

Start Date		Stop Date						
		Complete: yyyymmdd		Partial: yyyymm		Partial: yyyy		
		< 1 st dose	≥ 1 st dose	< 1 st dose yyyymm	≥ 1 st dose yyyymm	< 1 st dose yyyy	≥ 1 st dose yyyy	
Partial: yyyymm	= 1 st dose yyyymm	2	1	2	1	n/a	1	1
	≠ 1 st dose yyyymm		2		2	2	2	2
Partial: yyyy	= 1 st dose yyyy	3	1	3	1	n/a	1	1
	≠ 1 st dose yyyy		3		3	3	3	3
Missing		4	1	4	1	4	1	1

1 = Impute the date of first dose

2 = Impute the first of the month

3 = Impute January 1 of the year

4 = Impute January 1 of the stop year

Note: If the start date imputation leads to a start date that is after the stop date, then do not impute the start date. **For subjects who were never treated (first dose date is missing), partial start dates will be set to the first day of the partial month or first day of year if month is also missing.**

1. Imputation rules for partial or missing stop dates:
  - Initial imputation
    - a. For partial stop date mmYYYY, impute the last of the month.
    - b. For partial stop date YYYY, impute December 31 of the year.
    - c. For completely missing stop date, do not impute.
  - If the stop date imputation leads to a stop date that is after the death date, then impute the stop date as the death date.
  - If the stop date imputation leads to a stop date that is before the start date, then set the stop date as missing.
2. Imputation rules for partial or missing death dates:
  - If death year and month are available but day is missing:
    - a. If YYYYMM for the date last known to be alive equals YYYYMM for death date, set death date to the day after the date last known to be alive.

- b. If YYYYMM for the date last known to be alive is less than the YYYYMM for death date, set death date to the first day of the death month.
- c. If YYYYMM for the date last known to be alive is greater than YYYYMM for death date, data error, do not impute and censor subject survival time.
- If month and day are missing and year of death is known:
  - a. If YYYY for the date last known to be alive equals the YYYY for death date, set death date to the day after last known to be alive date.
  - b. If YYYY for the date last known to be alive is less than the YYYY for death date, set death date to the first day of the death year.
  - c. If YYYY for the date last known to be alive is greater than YYYY for death date, data error, do not impute and censor the subject survival time.
- If a death date is totally missing, do not impute and censor the subject survival time.

### 3. General Imputation rules for time to event efficacy endpoints

Unless otherwise specified, the partial/missing event dates will be imputed as follows:

- If event year and month are available but the day is missing:
  - a. If mmYYYY for the date last known to be event-free equals mmYYYY for event date, set event date to the day after the date last known to be event-free.
  - b. If mmYYYY for the date last known to be event-free is less than the mmYYYY for event date, set event date to the first day of the event month.
  - c. If mmYYYY for the date last known to be event-free is greater than mmYYYY for event date, data error and do not impute.
- If month and day are missing and year of event is known:
  - a. If yyyy for the date last known to be event-free equals the yyyy for event date, set event censor date to the date last known to be event-free.
  - b. If yyyy for the date last known to be event-free is less than the yyyy for event date, set OS censor date to last day of the prior year.
  - c. If yyyy for the date last known to be event-free is greater than yyyy for event date, data error and do not impute.

If an event date is totally missing, do not impute.

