### Duration of Response (DOR)

Duration of response is calculated for subjects who have achieved a response (PR or better). It is defined as time from the first observation indicating a response to the subsequent date of relapse, disease progression or death (due to any cause), whichever is earlier.

DOR time in months: (earliest date of relapse, disease progression or death - date of the first observation of response +1)/30.4

Subjects without relapse, disease progression or death until the analysis data cut-off date will be censored at the last adequate disease assessment date after first response; otherwise, at first response.

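### SAP Appendix A, item 3, censors a relapse or progression dated by year only, so a known failure is lost from duration of response

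*SAP*

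**What the plan says.** Appendix A, item 3, sets default rules for time-to-event efficacy endpoints: "Unless otherwise specified, the partial/missing event dates will be imputed as follows". When month and day are missing and the year is known, there are two workable branches:

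- **Branch a** (last known event-free in the same year as the event): "set event censor date to the date last known to be event-free".
- **Branch b** (last known event-free in an earlier year): "set OS censor date to last day of the prior year".

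Both give a censoring date. When only the day is missing, item 3 keeps the event. If the last event-free date falls in an earlier month, for example, the rule is "set event date to the first day of the event month".

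Item 2 of the same appendix handles deaths known only by year and keeps them as events. For the same year it says "set death date to the day after last known to be alive date"; for a later year, "set death date to the first day of the death year".

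SAP Section 5 ends a response at the "subsequent date of relapse, disease progression or death (due to any cause), whichever is earlier". Subjects with none of these "will be censored at the last adequate disease assessment date after first response", or at first response if there is no such assessment.

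SAP Section 9.5.2 (Table 3) plans Kaplan-Meier estimates for DOR. Section 10 drops PFS, EFS and TTR after early termination, but not DOR.

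**The concern.** Censoring says that failure had not been seen by that date and that the subject's later course is like that of subjects still at risk. A year-only relapse meets neither condition: the failure is recorded, and only its exact date is missing. Censoring it removes a failure from the Kaplan-Meier numerator and leaves the remaining responders to stand in for a subject who is known to have failed soon afterwards. DOR then looks longer than it was.

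The rule also makes event status depend on how complete the date is. A relapse recorded as a month and year counts; the same relapse recorded as a year alone does not. A programmer cannot satisfy both item 3 and the DOR definition, and in branch b must also guess whether OS means overall survival or the endpoint being analysed.

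**Working it through.** The documents state no figure that depends on this rule, so there is nothing to reproduce. The check has three steps.

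**1. Rules side by side**

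| Record | Rule | Status | Date |
|---|---|---|---|
| Relapse or progression, month and year known | Item 3 | Event | Imputed |
| Relapse or progression, year only, same year | Item 3, branch a | Censored | Last event-free date |
| Relapse or progression, year only, later year | Item 3, branch b | Censored | 31 December of the prior year |
| Death, year only, same year | Item 2 | Event | Day after last known alive |
| Death, year only, later year | Item 2 | Event | 1 January of the death year |
| Any relapse, progression or death | DOR definition | Event | Event date |

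The two censored rows are the exceptions.

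**2. Worked dates**

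SAP formula: DOR in months = (end date − first response date + 1)/30.4. Illustrative first response 1 March 2022, last event-free date 15 August 2022.

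- Event recorded as 2022. Branch a: censored at 15 August, (167 + 1)/30.4 = 5.53 months. Item 2 convention: event at 16 August, (168 + 1)/30.4 = 5.56 months.
- Event recorded as 2023. Branch b: censored at 31 December 2022, (305 + 1)/30.4 = 10.07 months. Item 2 convention: event at 1 January 2023, (306 + 1)/30.4 = 10.10 months.

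In each case the two conventions differ by one day in time and are opposite in status. The lost event is what matters.

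**3. Effect on Kaplan-Meier DOR**

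A small deterministic case: ten responders failing at 30, 60, …, 300 days. With all ten counted, the estimate reaches 0.5 at 150 days. Now censor the fifth failure 15 days early, at day 135. The estimate is still 0.6 after day 120, and five subjects are at risk at day 180, so it becomes 0.6 × 4/5 = 0.48. The median moves from 150 to 180 days. Kept as an event at day 136, the same record gives a median of 136 days.

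A simulation then compared the rules on the same data. Its assumptions are not in the documents: exponential DOR with true median 4 months, 18 months of follow-up, 5% to 25% of events dated by year only. Assessments every 28 days are as in SAP Section 3.1. Median DOR in months:

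| Responders | Year-only events | True dates | Item 3 | Item 2 convention |
|---|---|---|---|---|
| 10 | 5% | 3.45 | 3.72 | 3.45 |
| 10 | 10% | 3.45 | 4.00 | 3.49 |
| 10 | 25% | 3.52 | 5.00 | 3.55 |
| 20 | 5% | 3.75 | 4.01 | 3.72 |
| 20 | 10% | 3.78 | 4.34 | 3.75 |
| 20 | 25% | 3.75 | 5.20 | 3.72 |
| 200 | 5% | 4.01 | 4.21 | 3.98 |
| 200 | 10% | 3.98 | 4.51 | 3.91 |
| 200 | 25% | 3.95 | 5.26 | 3.78 |

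With 20 responders and 25% year-only events, the six-month estimate is 0.354 with true dates and 0.451 under item 3. With no year-only dates the rules agree exactly. The item 2 convention uses the earliest possible date, so it errs slightly low in places (3.78 against 3.95 in the last row), but far less than item 3 errs high.

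**The case against.** The strongest reply is that this will seldom occur. Disease response is assessed every 28 days until progression, whatever happens to treatment (SAP Section 3.1), and relapse is read from marrow and blood samples that normally carry full dates. Section 9.5.2 allows DOR tables and figures to be omitted below 10 events. The study ended early, selected analyses will go into a synopsis report, and no formal hypothesis is tested. All of this stands and limits the practical effect. It does not make the rule right: subject-level data are still to be provided when a summary is skipped, and a listing would carry the wrong status.

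Three stronger readings are tempting, and the documents do not support them.

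- **That branch b inflates DOR by censoring after the last event-free date.** Branch b applies only when the event year is later than the last event-free year. An event recorded in 2023 did not happen before 1 January 2023, so being event-free through 31 December 2022 follows from the record. Branch b never exceeds the true time, and the item 2 convention credits one day more. In the simulation, moving the censoring date back to the last event-free date changed the six-month estimate by at most 0.001. Few simulated records reached branch b, so the logical argument carries this point.
- **That a year-only death ending a response is an event under item 2 and censored under item 3.** Item 3 yields where something else is specified, and item 2 specifies death dates. The ordinary reading leaves deaths to item 2. What remains is that branch b names OS, whose only event is death, and so invites the conflict.
- **That one such record removes a third of the Part 4 events.** The 3 of 21 in Protocol Section 4.3.3 counts CR or CRi. DOR uses PR or better, and Protocol Table 2-1 shows four such Part 4 responders (one CRi at 120, one PR at 180, two CRi at 240 mg/m²), in interim data from a part planned for about 60 subjects.

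**Conclusion.** The rule is wrong as written for year-only relapse and progression. It turns a known failure into a censored time, contrary to the DOR definition and to item 3's own rule when the month is known, and out of line with item 2's treatment of deaths. The upward direction of the bias is clear and comes from the lost event, not from the censoring date.

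The size cannot be derived from the documents, which give no count of year-only dates. The simulated shifts show direction and a range under assumed inputs; they do not predict this trial's result. The likely effect is small. It falls on DOR, the only time-to-event efficacy endpoint in Table 3 that Section 10 does not drop. This is a low-severity correction that is worth making because it is specific and cheap.

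**What to change.** In Appendix A, item 3, for relapse or progression with only the year known:

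- **Branch a:** keep the event and date it the day after the last known event-free date.
- **Branch b:** keep the event, date it 1 January of the event year, and delete the reference to OS.
- Add one sentence saying that item 2 governs partial death dates for all endpoints.

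Any subject whose event date was imputed this way should be marked in the DOR listing. The cost is two amended lines and one added sentence. No new data are needed, and programming changes only if such records exist.
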